Metformin in Heart Failure (Met-HeFT)

[name] MD PhD, March 3rd 2020

Protocol Version 10

Main Study: IRB AAAR5389 (CUIMC)

PET Sub-study: IRB AAAR9360 (CUIMC)

HAZMAT (JRSC): APH-AAA26251

NCT 03331861

Summary of Protocol Changes from v.9

- We are modifying any hospitalization within the past 3 months as an exclusion criteria to any heart failure hospitalization within the past 3 months.**
- We are adding a stationary bicycle as a mode for performing a cardiopulmonary exercise test for patients who cannot or do not want to exercise on a treadmill.**

Summary of Protocol Changes from v.8

- Liver Function Tests were reclassified as a screening test from a baseline test since abnormal liver function is an exclusion criteria and not an outcome.
- Listing venous lactate as a baseline laboratory value to reflect Table 1 procedural timeline more accurately
- Specific statement that any laboratory value obtained for clinical purposes within three months of screening can be used for screening
- Removal of [name] from the DSMB and replacement with [name]

Summary of Protocol Changes from v.7

- Microbiome elements were removed from the protocol

Summary of Protocol Changes from v.6

- The PET radiotracers oxygen, palmitate and acetate are not available.
- The PET protocol is changed to just FDG and NH3, both of which are FDA approved.
- Change in effective radiation dose due to change in radiotracers
- We are pre-specifying a plan to pursue IRB/RDRC/JRSC approval for palmitate, acetate and oxygen when available from research radio-pharmacy to be started during active enrollment of the Met-HeFT trial.

Purpose:

This study evaluated the efficacy of metformin on myocardial function in non-diabetic patients with systolic heart failure. Fifty patients will be randomized to either metformin or placebo for 6 months in addition to regular therapy.

Hypothesis

The primary hypothesis is that metformin will improve myocardial performance in patients with

stable systolic heart failure without diabetes.

Endpoints

Primary endpoint: change in VE/VCO₂ over 6 months of treatment.

Secondary endpoints:

- a) heart failure decompensation (unscheduled office IV diuretic therapy, ED visit for decompensated heart failure or hospital admission for decompensated heart failure)
- b) Minnesota Health Living with Heart Failure Questionnaire Score
- c) LVEF,
- d) GLS and GCSR
- e) BNP
- f) body weight
- g) changes in dyspnea assessment score (VAS and 7-Likert scale),

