Plasma and serum (up to 50ml) will be stored for current and future analysis of biomarkers including but not limited to biomarkers of inflammation, endotoxemia/bacteremia, neurohormonal, immune and endothelial activation, angiogenesis, collagen turnover and congestion will be measured using established techniques. White blood cells may be isolated from collected blood, to assess patterns of inflammation and immune activation using established techniques. Additionally, novel biomarkers such as circulating microRNAs, non-coding RNAs may be utilized for biomarker analysis.

Dyspnea assessment: to be performed visual analogue scale (VAS) and seven-level Likert scale scores.

Echocardiogram: At baseline and final visit. The echocardiogram will be conducted according to the ASE Guidelines. M-Mode and two-dimensional (B-mode) imaging will be obtained from parasternal, apical and subcostal windows. LV dimensions will be measured at end systole and diastole from parasternal windows. EF will be calculated by Simpson's Biplane method. Right ventricular function will be assessed by tricuspid annular plane systolic excursion and right ventricular free wall excursion velocity on tissue doppler. Mitral valve inflow and tissue dopplers will be recorded to assess diastolic function. Speckle tracking echocardiography will be utilized to obtain global longitudinal strain and strain rate of all LV segments in four and two chamber views.

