The primary outcome in this study will be change in VE/VCO₂ slope. The VO₂ change outcomes will be assessed for normality using standard visual assessments (Q-Q plots and histograms) and statistical tests (Kolmogorov-Smirnov). If VE/VCO₂ slope change demonstrates evidence for non-normality, we will natural log transform values for our primary analyses. Prior to testing for differences, we will compare important clinical, laboratory and demographic characteristics between groups (treatment vs. control) to ensure that randomization achieved between groups balance on these important covariates. For variables that are unbalanced by treatment group (determined via statistically significant difference $p<0.05$), we will include these variables in multivariable models of the primary endpoint as described below. Linear regression models will be used to regress mean weight change on treatment group using intention-to-treat principles. If preliminary descriptive analyses indicate a need for multivariable models (see above), the relevant adjustments will be made to our regression models. Analysis of secondary outcomes will be conducted using contingency tables and Fisher's exact chi-square tests; for these outcomes, we will also utilize a modified Poisson regression model with robust error variance to assess the relative risk (separate regressions for each outcome). This modified Poisson model has been described previously and allows for multivariable models to be constructed should they be deemed necessary. Once a patient is randomized, they will be included in final analyses according to intention-to-treat principles regardless of whether they complete the study protocol. If patients are lost-to-follow up and final outcome assessments cannot be made we will use the "last observation carried forward" approach to assign a final outcome value. Additional sensitivity analyses will be performed by assigning final outcome values assuming patients in the treatment group had 10% lower mean weight loss and patients in the control group had 10% greater mean weight loss. This is very conservative approach that will inform the potential for differential outcomes according to follow-up status to explain our observed findings. However, we expect very little loss-to-follow up as these patients receive regular care at our center and are likely to return to the hospital regardless of continued study participation.

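### All secondary outcomes are assigned to contingency tables, Fisher's exact test and relative risks, but only one of the eight endpoints is binary and no cut-points are given for the others

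*Combined protocol and SAP*

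**What the plan says.** The Endpoints section lists eight secondary endpoints, (a) to (h). Endpoint (a) is "heart failure decompensation (unscheduled office IV diuretic therapy, ED visit for decompensated heart failure or hospital admission for decompensated heart failure"), and the Clinical Events paragraph records it as events. The rest are measurements or scores. Two are scores by name: endpoint (g) is given as "changes in dyspnea assessment score (VAS and 7-Likert scale"), while endpoint (b) is the "Minnesota Health Living with Heart Failure Questionnaire Score". The remaining five are peak VO₂ (h), body weight (f), BNP (e), the pair GLS/GCSR (d) and LVEF (c).

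The procedure descriptions agree with this. Dyspnoea is measured by "visual analogue scale (VAS) and seven-level Likert scale scores". For LVEF, "EF will be calculated by Simpson's Biplane method". Strain and peak VO₂ are likewise derived as numerical values.

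The Statistical Approach section then says: "Analysis of secondary outcomes will be conducted using contingency tables and Fisher's exact chi-square tests". For the same outcomes it adds a "modified Poisson regression model with robust error variance to assess the relative risk (separate regressions for each outcome"). The only linear model it names is this: "Linear regression models will be used to regress mean weight change on treatment group using intention-to-treat principles".

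**The concern.** Fisher's exact test on a two-by-two table and a relative risk both need a yes/no outcome. Seven of the eight endpoints are not yes/no, and the plan does not say how they would become so. Followed literally, the rule requires continuous scores to be dichotomised at cut-points that appear nowhere.

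Two things are at stake. A trial of 50 patients loses power if scores are split in two. And a cut-point chosen late is an open analyst choice, which raises the chance of a nominally significant result above that of one fixed cut. If the analyst instead uses t-tests, no power is lost, but the written method has been replaced by one that was not prespecified.

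**Working it through.** **1. Endpoints against methods.**

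| Endpoint | Type | Cut-point given? | Suitable stated method? |
|---|---|---|---|
| (a) HF decompensation | event | not needed | yes |
| (b) MLHFQ | score | no | no |
| (c) LVEF | continuous | no | no |
| (d) GLS, GCSR | continuous | no | no |
| (e) BNP | continuous | no | no |
| (f) body weight | continuous | no | possibly, the weight-change regression |
| (g) VAS, Likert | continuous, ordinal | no | no |
| (h) peak VO₂ | continuous | no | no |

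That is 1 binary endpoint and 7 that are not. Counting GLS/GCSR and VAS/Likert separately gives 10 measures: 1 binary, 1 ordinal and 8 continuous or score. The thresholds that do appear (for example LVEF at entry, and eGFR, lactate and glucose in the safety sections) serve eligibility or safety. None defines a response on (b) to (h).

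**2. The plan's own power figure.** There is none for a secondary endpoint. For the primary, the Power section gives a difference of 5, a spread of 6, alpha 0.05, 25 per arm and 83% power. Taking 6 as an SD, d = 5/6 = 0.833 and the noncentrality is 0.833 × √(25/2) = 2.946. Two-sided normal power is Φ(2.946 − 1.960) = 83.8%; the noncentral t gives 82.3%. Both agree with 83%. Taking 6 literally as a variance (SD 2.45) gives power near 100% and only 5 per arm for 83%, so the figure reproduces only with 6 as an SD.

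**3. Illustrative cost of dichotomising.** Assumptions: normal data, SD 1, 25 per arm, two-sided 0.05, and the pooled sample median as the cut. t-test power is exact; the other non-null figures come from 200,000 simulated trials per row.

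| d | t-test | Wilcoxon | Median split + Fisher |
|---|---|---|---|
| 0.5 | 41% | 38% | 19% |
| 0.83 | 82% | 80% | 52% |
| 1.0 | 93% | 92% | 69% |

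A fixed cut midway between the arm means at d = 0.833 gives proportions Φ(−0.417) = 33.8% and Φ(0.417) = 66.2%. Exact Fisher power is then 57.5%. On the two-proportion formula, 83% power would need 40 per arm, or 46 with continuity correction. A cut 1 SD beyond the control mean gives 45.0%, and one 1.5 SD beyond gives 30.4%.

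**4. Illustrative cost of leaving the cut open.** With a median split, the number above the cut in one arm is hypergeometric (50 patients, 25 above, 25 in the arm). Fisher's test rejects when that number is 17 or more, or 8 or fewer (p = 0.0227 at 17 and 0.089 at 16), so the exact null rejection rate is 2.3%. Taking the smallest p over five cuts (25th, 33rd, 50th, 67th and 75th percentiles) gives:

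- 4.9% with 37/33/25/17/13 patients above the cuts;
- 6.8% with mixed rounding;
- 8.4% with 38/34/25/16/12.

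**5. Can the Poisson model be used as it stands?** A log-link Poisson model with robust variance can be fitted to non-negative values as a ratio of means. With an assumed mean of 30 and SD of 6, its null rejection is 6.1% and its power is 44.3%, 84.5% and 94.3% at d = 0.5, 0.833 and 1.0. But that estimates a ratio of means, not the relative risk the plan names as its purpose, and it cannot take signed changes, which is how endpoint (g) is defined.

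**The case against.** **The linear models may be meant for continuous outcomes.** The linear-regression sentence names weight change, and the section opens by checking VO₂ change outcomes, in the plural, for normality. Read generously, body weight and peak VO₂ both gain a model. The weight sentence, however, directly follows text on the primary-endpoint models and may simply name the wrong outcome. The normality check leads to no test or model for peak VO₂. Even if both readings were granted, MLHFQ, LVEF, GLS/GCSR, BNP and dyspnoea would remain uncovered.

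**A seven-level score fits a contingency table.** True: a 2×7 exact test needs no cut-point. It ignores the ordering, though, and a relative risk still needs a cut.

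**The size is hypothetical.** This stands. The plan proposes neither a median split nor a search over cuts, and d = 0.83 is borrowed from another endpoint. The increase in null rejection starts from a conservative test, and the best-of-five range begins just under 5%. The figures show what is at risk; they do not predict what will happen.

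**The data for the remedy are not all clearly scheduled.** This stands in part. Table 1 marks vital signs at day 0 only, while the Data and Safety Monitoring Plan lists them at day 180 as well. The Echocardiogram paragraph does not mention GCSR by name. Both are already declared endpoints, so these are points to confirm; they do not remove the mismatch.

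**Conclusion.** The concern holds. As written, the method for secondary outcomes suits one of eight endpoints, or two if the weight regression is read as covering body weight. This is a stated method that does not fit the endpoints, rather than a missing detail. The count rests only on the endpoint list and the absence of cut-points. The power loss (82% to 52% at d = 0.83) and the null rejection of 4.9% to 8.4%, against 2.3% for a fixed median split, rest on assumed normal data, an effect size the plan does not give for these endpoints, and cut-points chosen for illustration; the inflation does not always exceed 5%. The primary analysis is untouched, so this should be corrected but does not threaten the main result.

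**What to change.** Revise the secondary-outcome text in Statistical Approach before unblinding:

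- **(a)** Keep Fisher's exact test and modified Poisson regression for this endpoint only, and define it as at least one qualifying event by day 180, yes or no.
- **MLHFQ, LVEF, GLS, GCSR, body weight, VAS, peak VO₂** Use a linear model of the day-180 value on treatment and baseline value, reporting the mean difference with a 95% CI. With baseline in the model, analysing change instead gives the same treatment estimate, so this also serves the change definition in (g).
- **BNP** Use the same model on the log scale, reported as a ratio of geometric means.
- **Seven-level Likert** Use either a proportional-odds model or a Wilcoxon test. Name one, and say whether it is applied to the day-180 level or to change.
- **Any dichotomised score** State the cut-point and its justification before unblinding.

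Prespecified t-tests or Wilcoxon tests on change would also cure the mismatch; baseline adjustment is preferred but not essential.

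The cost is SAP wording and routine programming. Table 1 already schedules MLHFQ, BNP, VAS/Likert, echocardiogram and CPET at days 0 and 180. Confirm that weight is recorded at day 180 and that GCSR will be derived from the echocardiograms.

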Patients will be randomized to either metformin or placebo. Metformin dose will begin with 500mg twice a day for the first two weeks and then increase to 1000mg twice a day for the remainder of the trial. In order to minimize GI side effects, the medication will be taken with a meal. The intervention will last 180 days. Prior to randomization all potential study subjects will be evaluated with complete medical history and brief physical examination, complete review of home medications, measurement of vital signs and body weight with calibrated scale, serum collection for basic metabolic panel, hemoglobin A1c and liver function test. All patients will also undergo cardiopulmonary exercise testing and transthoracic echocardiography. Patients who meet all the inclusion criteria will be required to complete the informed consent form. Patients will have 2 office visits in total, one at day 1 (baseline) and one on day 180 (final). On day 30, participants will have a blood work for basic metabolic panel, venous lactate and fasting plasma glucose for adverse event assessment (safety). On the final visit, patients will undergo repeat echo, labs and cardiopulmonary exercise testing. The timing of all procedures in this study is outlined in the table 1. Procedural timeline and further details of the relevant procedures are as follows:

Medical history and physical exam: Subjects will be asked to provide information about their basic demographics: age, gender, and race as well as previous and current health and medications. The subject will have his or her height, weight, blood pressure both supine and standing, heart rate, respiratory rate and body temperature recorded. A HF-focused physical examination will be performed and recorded. A Minnesota Living with Heart Failure Questionnaire will be completed.

Blood tests:

Blood be drawn via venipuncture. The following will be prospectively measured for every patient at the indicated time points.

- Screening: fasting insulin and glucose level, basic metabolic, liver function test and HgbA1c
- Baseline: , BNP, venous lactate
- Safety: basic metabolic panel, venous lactate and fasting glucose
- Final: basic metabolic panel, BNP

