Cardiopulmonary Exercise Test (CPET): At baseline and final visit. The CPET is to be performed on a either a treadmill with a Medgraphics Ultima metabolic cart or a Corival CPET Ergometer (stationary bicycle) in the Cardiopulmonary Exercise Lab. All testing is to be done in the Cardiopulmonary Exercise Lab in Milstein, a clinical cardiopulmonary exercise testing laboratory. There will be a physician present at all tests, and the appropriate emergency equipment and trained personnel are available should difficulties arise during the exercise test. The CPET will be conducted per ATS and AHA guidelines (25, 26). For a treadmill test: Participants will exercise on a treadmill at an increasing rate of 0.1MPH per minute and 1% grade per minute starting at a speed of 1.0 MPH at 0% grade. For a bicycle test: The participants will perform a 15 watt ramp protocol and instructed to pedal to a rate of 50-60 rpm. The protocol begins at zero watts and will increase in resistance by either 15 watts/minute (for female patients) or 20 watts/minute (for male patients) Heart rate, BP and perceived exertion score (RPE, reported on a scale from 0-10.0) will be recorded in one-minute intervals. Oxygen consumption (VO2) (ml/min), Carbon Dioxide production (VCO2) (ml/min), and minute Ventilation (VE) (L/min) will be measured on a

breath by breath basis. Peak VO₂, VE/VCO₂ and respiratory exchange ratio (RER) will be computed.

Biobank: Serum samples will be stored in a biobank repository in the CCTI Biobank Core Facility. The purpose of this biobank is to characterize serum biomarkers of patients with heart failure who have been exposed to metformin versus placebo. The registry will include previously gathered clinical information in electronic medical records. This data includes demographics, clinical comorbidities, hemodynamics, echocardiographic indices of structure and function, hospitalizations, medication use and laboratory data. All specimens/data will be distributed at the discretion of the principal investigator. The purpose of this dissemination will be for experimental collaboration. We will review to make sure collaborators have an existing approved IRB before we distribute. The proper MTA will be executed prior to delivery of samples. All samples will be coded so the recipient will not have any direct patient identifiers linked to these samples.

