Power for VE/VCO₂: We base the sample size calculation on data from Wong et al (31). We estimate the average effect size of metformin on the slope of VE/VCO₂ to be -5 with a starting average slope of 32 and a variance of 6. In order to achieve 83% power with an alpha of 0.05, we will enroll 25 patients in each arm.

Positron Emission Tomography (PET) Sub-study (IRB AAAR 9360)

The goal of this sub-study is to enroll patients to undergo cardiac PET imaging before and after treatment with either metformin or placebo. In this pilot sub-study, we will recruit patients at the time of their enrollment into Met-HeFT to undergo serial PET scans with metabolic tracers. We will specifically use FDA approved radiotracers for this study including ¹⁸F-Fluorodeoxyglucose (¹⁸F-FDG) to track myocardial glucose consumption and ¹³N-ammonia (¹³N-NH₃) to track perfusion. With these combination of radiotracers, we will be able to quantitatively measure myocardial metabolism and its reliance on different pathways that may be influenced by metformin.

Consecutive patients in Met-HeFT will be recruited at the time they are enrolled in the trial to be included in the sub-study. The decision to enroll in this sub-study will have no effect on their enrollment in Met-HeFT. After enrollment, patients will undergo a PET scan using two radiotracers: ¹⁸F-FDG and ¹³N-ammonia. Scans will occur prior to initiation of the study drug and at the 6 month end of study mark. Patient randomization will be maintained and both the study participants, coordinators and investigators will be blinded to patient assignment.

Inclusion/Exclusion Criteria: Any patient enrolled and meeting all inclusion criteria for Met-HeFT will be eligible to elect for inclusion into this sub-study.

Pregnancy Test: Women of childbearing potential will provide a urine specimen to determine if they are pregnant. Pregnant women will be excluded from the study. The source of the urine specimen will be from Columbia and/or NYPH Subjects/Patients or repositories managed by Columbia. The specimen will be labeled with direct identifiers.

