Congenital Abnormality	Pregnancy is an exclusion criteria for this study and patients will be advised not to become pregnant during this study. However, if we detect a pregnancy that occurs during the study (there is a pregnancy test at the end of study), we will stop the study for that patient. We will mandate that we follow the patient until after birth to determine if there is a congenital abnormality. If we detect this event, the DSMB will be required to unblind the allocation (if the trial is ongoing) and determine if the congenital abnormality is related to the study drug.
Hospitalization	Discontinuation of study drug if it is either 1) unsafe to continue for medical reasons by either the treating physicians, the PI of the study, or the DSMB, or 2) if it deemed by the DSMB to be related to the study drug. The DSMB will unblind the allocation and determine if the hospitalization is related to the study drug.
Venous Lactate rises to $>2\text{mmol/L}$	Discontinue study drug, de-identification of study medication. Repeat lactate daily until normalizes. Contact primary cardiologist. Consider inpatient hospitalization.
Fasting Serum Glucose <60mg/dL	Discontinue current regimen. Administer patient oral glucose. Repeat value until normalizes. Referral to primary physician/cardiologist. Referral to ED if for referral or assessment if symptomatic and non-responsive to glucose tabs.

Renal Impairment for already enrolled patients

Glomerular Filtration Rate	Action
GFR \geq 45ml/min/1.73m ²	No action
GFR 30 - 44ml/min/1.73m ²	Reduce total dosage to 500mg twice a day. Schedule follow up basic metabolic panel in 3 months if GFR measurement occurs >3 months from scheduled end of trial. If follow up GFR is greater than 45 ml/min/1.73m ² , then patient can revert dosage to 2 grams per day. If GFR is less than 30 ml/min/1.73m ² , study drug and patient enrollment will be terminated.
GFR <30ml/min/1.73m ²	Stop Drug and patient enrollment in trial

5. Reporting of adverse events/adverse drug reactions

Adverse events (AEs) will be reported to the IRB and the DSMB. Adverse events will be reported on a weekly basis to the DSMB and serious adverse events will be reported to the IRB and DSMB within 24 hours of being detected.

6. Who will review AEs and other safety data?

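### With VE/VCO₂ measured only at baseline and day 180, LOCF scores every missing final test as zero change, and the only sensitivity rule is written for weight loss

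*Combined protocol and SAP*

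**What the plan says.** The primary outcome is the change in VE/VCO₂ slope over six months. The CPET paragraph sets two measurements: "Cardiopulmonary Exercise Test (CPET): At baseline and final visit". Table 1 marks the test at days 0 and 180 only. Under Study Intervention and Procedures, day 30 is blood work only, and no exercise test is scheduled for patients who stop early.

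The Statistical Approach keeps everyone in the analysis: "Once a patient is randomized, they will be included in final analyses according to intention-to-treat principles regardless of whether they complete the study protocol". For missing outcomes it says: "If patients are lost-to-follow up and final outcome assessments cannot be made we will use the 'last observation carried forward' approach". The one sensitivity analysis fills in final values "assuming patients in the treatment group had 10% lower mean weight loss and patients in the control group had 10% greater mean weight loss". The plan describes it this way: "This is very conservative approach that will inform the potential for differential outcomes according to follow-up status". Loss to follow-up is expected to be very small; no rate is given.

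The renal impairment table under the Data and Safety Monitoring Plan gives, for GFR below 30: "Stop Drug and patient enrollment in trial".

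**The concern.** With one post-baseline measurement there is nothing between baseline and day 180 to carry forward. LOCF here means imputing no change, with certainty, for each patient without a final test. That shrinks a real effect and hides any deterioration in those who leave. It is not reliably cautious: if both arms improve and placebo loses more patients, zeros pull the placebo mean up and create an apparent benefit of metformin.

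The sensitivity analysis should expose this and does not. Body weight is only a secondary endpoint. For VE/VCO₂ the rule has no unit, no direction and no stated mean to which the 10% applies, so an analyst would have to choose a reading after the data are in.

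The plan can also create the missing values itself. Ending a patient's enrolment on a renal criterion, while keeping that patient in the intention-to-treat analysis, leaves a randomised patient with no day-180 test unless one is arranged.

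**Working it through.** **Inputs.** From Power for VE/VCO₂: 25 per arm, difference -5, α 0.05, power 83%, and a spread given as "with a starting average slope of 32 and a variance of 6". Assumed, because the plan is silent: 1, 2 or 5 missing per arm (4%, 8%, 20%), placebo change 0, values missing at random. Rejection rates come from simulation (40,000 trials, pooled t-test on change).

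**The plan's own figure.** With 6 taken as the SD, power = Φ(5 / (6√(2/25)) − 1.96) = Φ(2.95 − 1.96) = 83.8%; the t-test gives 82.3%. This reproduces 83%. With 6 taken as a variance (SD 2.45), power exceeds 99.9%. SD 6 is therefore used below.

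**LOCF.** With missing fractions m_T, m_C and true mean changes μ_T, μ_C, the expected difference is (1 − m_T)μ_T − (1 − m_C)μ_C.

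| Missing per arm | Expected difference (true -5) | Null rejection |
|---|---|---|
| 1 | 0.96 × (-5) = -4.8 | 4.8% |
| 2 | 0.92 × (-5) = -4.6 | 5.0% |
| 5 | 0.80 × (-5) = -4.0 | 5.1% |

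At 5 missing per arm, power is 71% under LOCF and 73% in completers, so most of the loss from about 83% comes from the missing data rather than from LOCF.

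**Unequal dropout, no true difference.** Both arms change by -5; 5 placebo and 0 metformin patients are missing. LOCF gives -5 − 0.8 × (-5) = -1.0. It rejects in 8.7% of trials, 8.3% in favour of metformin (nominal 2.5%). With 2 placebo patients missing the bias is -5 − 0.92 × (-5) = -0.4.

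**The 10% rule carried over to VE/VCO₂, 5 missing per arm, true -5 against 0.**

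- *Own-arm mean.* Missing metformin values are 0.9 × (-5) = -4.5 and missing placebo values 1.1 × 0 = 0. Difference: 0.8 × (-5) + 0.2 × (-4.5) = -4.9. Null rejection is 11.9% (5.9% and 7.2% at 1 and 2 missing), because single mean values understate variance. Power is 84%, above LOCF and completers.
- *Pooled mean of -2.5.* Missing values are -2.25 and -2.75. Difference: (-4.0 − 0.45) − (0 − 0.55) = -3.9. Null rejection is 5.2%.
- *Own-arm mean shifted by 10% of the baseline slope, 3.2.* Missing values are -1.8 and -3.2. Difference: (-4.0 − 0.36) − (-0.64) = -3.7, with power 62%.

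The own-arm reading is not always the more permissive: with 5 missing on placebo only, power is 83% under it and 86% under LOCF. A literal variance of 6 leaves the LOCF bias unchanged and gives own-arm null rejection of 6.2%, 7.0% and 11.8%.

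**Proposed replacement.** Multiple imputation from arm and baseline slope (3,000 trials, 20 imputations, assumed baseline SD 6 and correlation 0.5) gives -5.01, -4.95 and -5.04 at 1, 2 and 5 missing per arm, with null rejection 4.5%, 5.0% and 5.4%. In the unequal-dropout case it gives -0.01 with 4.6% rejection.

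**Its limit.** Suppose there is no drug effect, but 5 metformin and 1 placebo dropouts would have worsened by 8 (assumed). The true difference is 0.2 × 8 − 0.04 × 8 = +1.28. LOCF gives 0 and missing-at-random imputation about 0 (+0.05). Adding a delta of +8 to missing metformin values gives 0.2 × 8 = +1.6.

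**The case against.** At the dropout the plan expects, LOCF does little harm. With 1 or 2 missing per arm the bias is 0.2 to 0.4 against a standard error of about 1.65, type I error stays near 5%, and power is within about a point of completers. The striking figures need 20% missing. The false-benefit case also needs placebo to improve by the full 5 and all the losses to fall on placebo; if five losses fell at random among 50 patients, that split has probability 2.5%. Five losses on metformin instead would give +1.0, against the drug. All of this stands and limits the size of the point.

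The LOCF sentence speaks of patients lost to follow-up, not of deaths or ended enrolment. That is so, but every randomised patient must be analysed and no other rule is offered.

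The weight wording may be a slip, since the main regression sentence also names weight change, and on some readings the rule is indeed more conservative than LOCF. The secure finding is therefore that the rule is undefined, and that the description as very conservative fails on at least one natural reading.

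With only the final value missing, completer regression adjusted for the same baseline covariates is also unbiased under missing-at-random. That is correct; imputation is preferred because it keeps all randomised patients and carries the delta analysis.

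Clinical Data Collection promises follow-up until death, but by extracting records, which schedules no exercise test.

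**Conclusion.** The concern holds. Zero change under LOCF follows exactly from the visit schedule and needs no assumption. That the sensitivity rule cannot be run for the primary endpoint follows from its wording.

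The size depends on a dropout rate the plan does not give. The LOCF bias is minor at 1 or 2 missing per arm. It becomes material at roughly 10% or more, or when missingness differs between arms, and it can go in either direction. The harm is a biased estimate with no usable check on it, rather than a general inflation of type I error. The plan should be changed before unblinding; the point does not threaten the design.

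**What to change.** 1. Replace LOCF with multiple imputation of day-180 VE/VCO₂ under missing-at-random, using arm, baseline slope and baseline covariates already collected. Then fit the primary regression in all randomised patients, naming VE/VCO₂ as its outcome.
2. Replace the 10% weight-loss rule with a delta-adjusted tipping-point analysis in slope units: make missing metformin values progressively worse until the conclusion changes. This step, not the imputation, addresses worsening among dropouts.
3. State how deaths before day 180 are scored and which patients the missing-data rule covers.
4. Reconcile the ending of enrolment in the renal table with the intention-to-treat statement, so that the day-180 test is sought from every willing randomised patient. No drug-stopping rule is altered.

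The cost is SAP wording, some programming, and booking a final test for willing patients who have stopped study drug. Intervals will be wider than under LOCF, which treats imputed zeros as data. At 5 missing per arm the completer standard error is 6√(2/20) = 1.90. Under LOCF it is √((5.73² + 5.37²)/25) = 1.57, where 5.73 and 5.37 are the arm SDs once zeros are filled in. That is about 20% wider; with 1 or 2 missing the difference is small.
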